## **Brentuximab vedotin (ADCETRIS®)**

### **Clinical Study Protocol C25003 Amendment 7, EudraCT: 2011-005450-60**

functional imaging typically obviates the need for a flexible number of cycles (6-8), and European Society for Medical Oncology (ESMO) and other guidelines are in the process of being updated to reflect this evolving information. Six cycles was thus selected as the duration of frontline therapy in this study.

Notably, this trial does not prospectively plan for patients, even those with bulky disease, to receive radiation therapy. It instead follows the model recently presented by Engert et al as used in the German Hodgkin Study Group (GHSg) HD15 trial. In that study, patients in partial response (PR) with a persistent mass measuring 2.5 cm or more upon completion of frontline chemotherapy were assessed by PET. Only patients who were positive on centrally-reviewed PET scan received additional radiotherapy with 30Gy, yet these data show that frontline therapy was successful. Although the GHSg HD15 study investigated 3 various BEACOPP regimens, this approach to radiotherapy has also been recommended for use with ABVD and seems to strike an appropriate compromise between therapeutic benefit and reducing the risk of later malignancy secondary to radiation exposure.

#### **1.5 Potential Risks and Benefits**

As detailed in Section 1.3, brentuximab vedotin monotherapy has demonstrated therapeutic activity in CD30+ hematological malignancies.

Brentuximab vedotin treatment causes a peripheral neuropathy that is predominantly sensory. Cases of peripheral motor neuropathy have also been reported. Brentuximab vedotin-induced peripheral neuropathy is typically cumulative and generally reversible. In the SG035-0003 and SG035-0004 clinical studies, 54% of patients experienced neuropathy of any grade. Of these patients, 49% had complete resolution, 31% had partial improvement, and 20% had no improvement. Of the patients who reported neuropathy, 51% had residual neuropathy at the time of their last evaluation. Monitoring patients for symptoms of neuropathy, such as hypoesthesia, hyperesthesia, paresthesia, discomfort, a burning sensation, neuropathic pain or weakness is required. Patients experiencing new or worsening peripheral neuropathy may require brentuximab vedotin dose modifications, including a dose delay (see Table 6-1).

Infusion-related reactions, including anaphylaxis, have occurred with brentuximab vedotin. Monitoring of patients during infusion is required. If anaphylaxis occurs, the administration of brentuximab vedotin should be immediately and permanently discontinued and appropriate medical therapy administered. If an infusion-related reaction occurs, the infusion should be interrupted and appropriate medical management instituted. Patients who

**Brentuximab vedotin (ADCETRIS®)**

**Clinical Study Protocol C25003 Amendment 7, EudraCT: 2011-005450-60**

have experienced a prior infusion-related reaction should be premedicated according to institutional guidelines for subsequent infusions. Premedication may include acetaminophen, an antihistamine and a corticosteroid.

Clinically significant laboratory abnormalities were to be reported as adverse events per the phase 2 study protocols. Central laboratory data were collected only predose for each treatment cycle. Few patients overall had postbaseline worsening to Grade 3 or higher in clinical laboratory values. The clinical laboratory parameters for which the most patients had new or worsening shifts to  $\geq$ Grade 3 were low neutrophils (11%), lymphocytes (11%), platelets (6%), leukocytes (5%), and high glucose (6%). Only 1 patient in the phase 2 studies had Grade 3 ALT and AST.

Any treatment that can decrease immune function may contribute to malignancy and infections; patients are to be monitored for these events during the treatment period and up to and including 30 days after the last dose of frontline therapy.

Complete blood counts should be monitored prior to each dose of brentuximab vedotin and more frequent monitoring should be considered for patients with Grade 3 or 4 neutropenia. Prolonged ( $\geq$ 1 week) severe neutropenia can occur. If Grade 3 or 4 neutropenia develops, manage by dose delays, reductions, or discontinuations (see [Table 6-1](#)).

Tumor lysis syndrome may occur. Patients with rapidly proliferating tumor and high tumor burden are at risk of tumor lysis syndrome and should be closely monitored. If tumor lysis syndrome occurs, take medically appropriate measures.

Stevens-Johnson syndrome has been reported with brentuximab vedotin. If Stevens-Johnson syndrome occurs, brentuximab vedotin must be discontinued and the appropriate medical therapy administered.

Progressive multifocal leukoencephalopathy (PML) has been reported with brentuximab vedotin use. PML is a rare demyelinating disease of the brain that is caused by the John Cunningham virus (JCV). It typically occurs in immunocompromised individuals and can be fatal. Presenting features may include altered mental status, motor deficits such as hemiparesis or ataxia, visual disturbances, or higher cortical dysfunction such as dysphasia or agnosia. Seizures have also been reported in patients with PML (approximately 20%). The onset of neurological deficits may occur over weeks to months. Cognitive decline without accompanying deficits in motor or sensory function is uncommon. Optic nerve involvement, fever, and spinal cord disease are not typically associated with PML. In

## **Brentuximab vedotin (ADCETRIS®)**

### **Clinical Study Protocol C25003 Amendment 7, EudraCT: 2011-005450-60**

addition, peripheral neuropathy, which has been reported with brentuximab vedotin treatment, is not commonly reported with PML. If PML is suspected, a diagnostic work-up should be performed, as described in Section 6.6.

Acute pancreatitis has been reported in patients treated with brentuximab vedotin and has contributed to fatal outcomes in some cases. Onset typically occurred after 1 to 2 doses of brentuximab vedotin. Early symptoms included severe abdominal pain, nausea, and vomiting. The majority of pancreatitis cases were complicated by other possible contributory factors, including cholelithiasis and alternate etiologies (eg, pancreatic lymphoma progression, displacement of bile duct stent, etc.).

Approximately 1% of patients treated with brentuximab vedotin in the investigational or commercial setting have had an AE that was suggestive of a hepatobiliary disorder. The majority of events occurred after 1 to 2 treatment cycles and they were characterized by asymptomatic mild to moderate transient elevations in ALT and AST. Elevated liver enzymes were observed upon rechallenge for some patients.

Preliminary population PK analyses of the effects of renal impairment on brentuximab vedotin metabolism suggest that no dose adjustments are necessary for patients with moderate renal impairment. Additional analysis is planned to more fully characterize the pharmacokinetics in these patient populations.

Monomethyl auristatin E (MMAE) is primarily metabolized by CYP3A. Coadministration of brentuximab vedotin with ketoconazole, a potent CYP3A4 inhibitor, increased exposure to MMAE by approximately 34%. Patients who are receiving strong CYP3A4 inhibitors concomitantly with brentuximab vedotin should be closely monitored for adverse reactions. Coadministration of brentuximab vedotin with rifampin, a potent CYP3A4 inducer, reduced exposure to MMAE by approximately 46%.

The effects of brentuximab vedotin on embryogenesis, reproduction, and spermatogenesis in humans are unknown. In addition, data about the effects of brentuximab vedotin in pregnant women are unavailable. Please see Section 6.5 for appropriate precautions triggered by the administration of study medication.

## **2. STUDY OBJECTIVES**

### **2.1 Primary Objective**

- To compare the modified progression-free survival (mPFS) obtained with brentuximab vedotin (ADCETRIS®) plus AVD (abbreviated A+AVD) versus that obtained with ABVD for the frontline treatment of advanced classical HL

### **2.2 Secondary Objectives**

The key secondary objective is

- To determine if A+AVD improves OS versus that obtained with ABVD

Other secondary objectives are:

- To determine if A+AVD improves CR rate versus that obtained with ABVD
- To determine the safety profile of A+AVD relative to that of ABVD
- To determine the event-free survival (EFS) obtained with A+AVD and ABVD
- To determine the disease-free survival (DFS) rate obtained with A+AVD and ABVD
- To determine if A+AVD improves overall ORR (defined as CR + PR) versus that obtained with ABVD
- To determine the DOR and duration of complete remission (DOCR) obtained in the A+AVD and ABVD arms
- To determine the rate of patients receiving irradiation for HL not in CR in the A+AVD and ABVD arms
- To determine the rate of patients in CR at the end of frontline therapy in the A+AVD and ABVD arms
- To determine the rate of Cycle 2 PET negativity in patients treated with A+AVD versus those treated with ABVD
- To determine if A+AVD improves health-related quality of life (HRQOL) versus ABVD

## **Brentuximab vedotin (ADCETRIS®)**

### **Clinical Study Protocol C25003 Amendment 7, EudraCT: 2011-005450-60**

- To describe the PK of brentuximab vedotin, MMAE, and total antibody (TAb) in blood
- To determine the immunogenicity of brentuximab vedotin

### **2.3 Exploratory Objectives**

The exploratory objectives are:

- To investigate any differences in lung-specific patient-reported outcomes (PROs) between the treatment arms
- To assess any impact of brentuximab vedotin dosing on serum concentrations of AVD
- To investigate any differences between the treatment arms in the rate of patients alive without HL at 3 and 5 years (see Section 8.1.6.3 for definition)
- To assess changes in tumor biomarker expression before and after treatment
- CCI [REDACTED]  
[REDACTED]  
[REDACTED]
- To assess other PROs
- To assess medical resource utilization
- To assess fertility

### **3. STUDY ENDPOINTS**

#### **3.1 Primary Endpoints**

The primary endpoint is

- Modified PFS per IRF assessment using the Revised Response Criteria for Malignant Lymphoma

#### **3.2 Secondary Endpoints**

The key secondary endpoint is

- OS

Other secondary endpoints are:

- Rate of CR as best overall response achieved at the end of randomized regimen (A+AVD or ABVD) per IRF assessment using the Revised Response Criteria for Malignant Lymphoma
- AEs, SAEs, assessments of clinical laboratory values, and vital sign measurements
- EFS
- DFS
- ORR
- DOR per IRF
- DOCR per IRF
- The rate of patients not in CR that received irradiation
- CR rate per IRF at the end of frontline therapy
- The rate of Cycle 2 PET negativity
- PRO per European Organization for Research and Treatment of Cancer (EORTC) QLQ-C30

**Brentuximab vedotin (ADCETRIS®)**

**Clinical Study Protocol C25003 Amendment 7, EudraCT: 2011-005450-60**

- PK parameters for brentuximab vedotin, MMAE, and TAb
- The presence of antitherapeutic antibodies (ATA) to brentuximab vedotin

**3.3 Exploratory Endpoints**

The exploratory endpoints are:

- PRO per FACIT-Dyspnea 10
- Serum concentrations of AVD in a subset of ABVD- and A+AVD-treated patients, respectively
- Percent of patients alive without HL at 3 and 5 years
- Percent of patients switching therapy post Cycle 2 pre-End of Treatment (EOT)
- CCI [REDACTED]
- CCI [REDACTED]
- PRO per FACT-Ntx (Abbreviated)
- Patient-reported health utility values per EQ-5D
- Utilization of medical resources
- Incidence of pregnancy (patients or partners of patients) in each treatment arm at time of study closure

## **4. STUDY DESIGN**

### **4.1 Overview of Study Design**

This open-label, randomized, 2-arm, multicenter, phase 3 study has the primary objective of comparing the mPFS obtained with A+AVD against that obtained with ABVD. For this study, the definition of PFS has been modified to include the receipt of anticancer chemotherapy or radiotherapy for patients not in CR after the completion of frontline therapy as a progression event in addition to the customary events of disease progression or death due to any cause (a definition of completion of frontline therapy is provided in [Table 8-1](#)).

The study will enroll approximately 1240 patients; enrollment is anticipated to last 3 years. All enrolled patients must have a histologically-confirmed diagnosis of Stage III or IV classical HL that has not been previously treated with systemic chemotherapy or radiotherapy. Patients will be stratified by region (Americas vs Europe vs Asia) and number of International Prognostic Factor Project (IPFP) risk factors (0-1 vs 2-3 vs 4-7). (IPFP risk factors are listed in [Section 15.5](#).)

Patients will be randomized 1:1 into 1 of 2 treatment arms, for a total of approximately 620 patients per arm:

- A+AVD: Brentuximab vedotin 1.2 mg/kg plus doxorubicin 25 mg/m^2, vinblastine 6 mg/m^2, dacarbazine (DTIC) 375 mg/m^2.
- ABVD: Doxorubicin 25 mg/m^2, bleomycin 10 units/m^2, vinblastine 6 mg/m^2, dacarbazine (DTIC) 375 mg/m^2.

A+AVD and ABVD will be administered intravenously on Days 1 and 15 of each 28-day cycle. Brentuximab vedotin will be administered intravenously over 30 minutes at a dose of 1.2 mg/kg; the brentuximab vedotin infusion is to be started within approximately 1 hour after completion of AVD therapy. Patients may receive up to 6 cycles of therapy (A+AVD or ABVD).

Response to treatment and disease status assessments will be evaluated according to the Revised Response Criteria for Malignant Lymphoma by an IRF that will be blinded to patients' treatment. Tumor measurements will be assessed (CT and PET scans) at screening, after completion of Cycle 2 (Cycle 2 Day 25 ± 1 day), and at 3 to 7 weeks after the last dose of frontline therapy. CT scans only will be used for the disease assessment follow-up,

**Brentuximab vedotin (ADCETRIS®)****Clinical Study Protocol C25003 Amendment 7, EudraCT: 2011-005450-60**

performed every 3 months during the first year of posttreatment disease follow-up, then every 6 months until study closure (5 years after the last patient is enrolled). If, for any reason other than death or documented disease progression, a patient discontinues randomization therapy (A+AVD or ABVD) after Cycle 2 Day 25 but before completion of randomization therapy, every effort must be made to obtain PET and CT scans prior to initiation of subsequent therapy for HL. Responses and relapses will be assessed by an IRF. Evaluations will be performed until progressive disease (PD) is documented, receipt of second-line anticancer therapy for HL (including chemotherapy or radiation), death occurs, or the end of study. Patients will be followed for survival until death or for a minimum of 5 years after enrollment of the last patient.

Deauville scoring (see Section 15.6) per IRF will be used to evaluate the results of patients' Cycle 2 Day 25 PET/CT. Patients whose disease earns a Deauville score of 4 or less will continue study drug treatment according to their randomized arm (ABVD or A+AVD). Patients whose PET-positive disease earns a score of 5 may, at the investigator's discretion, receive an alternative regimen (physician's choice) for the remainder of planned frontline therapy. Patients with a Deauville score of 5 who, at investigator's discretion, are taken off study drug will be continue to be followed for response assessment; switching therapy prior to completion of frontline therapy will not be considered an mPFS progression event. Of further note, any switch in therapy prior to completion of frontline therapy will not be considered an mPFS event.

An interim futility analysis will be conducted when the first approximately 348 patients have completed the regimen to which they were randomized (ie, received the planned study drug regimen with no more than 2 missed doses of A+AVD or ABVD) or have discontinued treatment prior to completion. The final analysis of the mPFS primary endpoint will be conducted when 260 mPFS events occur; an interim analysis of OS will also be conducted at that time. The final analysis of OS will be conducted when 112 deaths occur, approximately 4 years after randomization of the last patient.

Safety will be evaluated according to National Cancer Institute Common Terminology Criteria for Adverse Events (NCI CTCAE) version 4.03, effective 14 June 2010, and by measuring changes from baseline in the patient's vital signs, ECOG performance status, electrocardiogram (ECG), and clinical laboratory results. Safety data will be periodically reviewed by an independent data monitoring committee (IDMC) per the IDMC charter.

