#### **6.4 Permitted Concomitant Medications and Procedures**

The following medications and procedures are allowed during the study:

- For patients with a Deauville score of 5 upon Cycle 2 Day 25 PET scanning, physician's choice of alternative therapy is permitted, but not required, for the remainder of frontline treatment.
- Radiotherapy based on end-of-frontline therapy PET scanning: Patients in PR upon completion of frontline chemotherapy with PET-positive disease may receive radiotherapy.
- The use of topical, inhalational and ophthalmic steroids is permitted. Corticosteroids are permitted as part of a chemotherapy premedication regimen or for the treatment of HL per institutional standards.
- Patients may receive concomitant hormonal therapy provided they have been on a stable dosage for at least 1 month prior to enrollment. No restrictions are placed upon the use of birth control.
- The use of platelet and/or red blood cell supportive growth factors or transfusions when applicable is allowed.
- The use of colony stimulating factors for the treatment of neutropenia per institutional practice is permitted during therapy.

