## **Brentuximab vedotin (ADCETRIS®)**

### **Clinical Study Protocol C25003 Amendment 7, EudraCT: 2011-005450-60**

every 6 months until the first of disease progression or study closure. CT scans are required every 12 weeks ( $\pm 1$  week) until 12 months of PTFU and then every 6 months ( $\pm 2$  weeks) until study closure. For patients who have PD, survival/disease status and information regarding the initiation of an alternative lymphoma treatment may be obtained by phone call. To support fertility assessment, any pregnancy occurring in patients or their partners from the date of first dose until the date of study closure should be reported.

Patients who stop treatment for any reason other than PD will continue to have mPFS follow-up visits until the occurrence of PD; the patient withdraws consent for further follow-up; or, the start of another anticancer therapy for patients not in CR after completion of frontline therapy.

Patients will be followed for survival until 5 years from the date of the last patient randomized, or death, whichever occurs first. Survivor information may be collected by methods that include, but are not limited to, telephone, e-mail, mail, or retrieved from online or other databases (eg, social security indexes). In addition, the start of another anticancer therapy will be collected.

See the [Schedule of Events](#) for appropriate assessments during follow-up.

NOTE: Related SAEs must be reported to the Millennium Department of Pharmacovigilance & Risk Management or designee. This includes deaths that the investigator considers related to study drug that occur during the posttreatment follow-up. Refer to Section 10 for details regarding definitions, documentation, and reporting of SAEs.

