#### **8.1.1 Determination of Sample Size**

The primary endpoint of the study is mPFS, and the study is powered on the following assumption: a 2-year mPFS of 81% for patients in the A+AVD treatment group versus 73% for patients in the ABVD treatment group (HR=0.67; assuming a decrease in the PFS event rate after 2 years). A total of 260 mPFS events will provide 90% power to detect a hazard ratio of 0.67 at a 1-sided significance level of 0.025 using a log-rank test. Approximately 1240 patients will be randomized to achieve (with 95% probability) 260 mPFS events in approximately 60 months, assuming 36 months of accrual, a 5% annual dropout rate, and 24 months of mPFS follow-up after last patient in.

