5.8.1.2 Handling of Missing Assessment and Censoring for mPFS Primary Analysis

The determination of the date of progression by the IRF will be used for the primary analysis. Sensitivity analyses will also be performed to evaluate the robustness of results.

For the mPFS primary analysis, disease assessment data should be collected according to the intended schedule of assessment, and the date of progression should be assigned based on the time of the first evidence of disease progression regardless of violations and

Brentuximab vedotin (ADCETRIS™)
Statistical Analysis Plan, Study C25003

discontinuation of study drug. For those patients who receive new anticancer chemotherapy or radiotherapy for HL after completion of frontline therapy without confirmed noncomplete-response, mPFS will be determined by PD or death. Detailed handling rules for missing assessments and censoring for the analysis of mPFS are presented in [Table 5-2](#).

Table 5-2 Handling of Missing Assessments and Censoring for mPFS Primary Analysis

Situation	Date of Progression or Censoring	Outcome
No baseline and/or no postbaseline assessment, no subsequent anticancer therapy after frontline therapy, no death	Date of Randomization	Censored
Disease progression documented between scheduled visits	Date of next scheduled visit	Progressed
No documented mPFS event	Date of last adequate assessment ^a	Censored
Lost to follow-up, withdraw consent before any documented mPFS event	Date of last adequate assessment ^a	Censored
Treatment discontinuation for undocumented disease progression after the last adequate assessment	Date of last adequate assessment ^a	Censored
mPFS event after more than one missed visit	Date of last adequate assessment ^a	Censored

a Adequate assessment is defined as there is sufficient data to evaluate a patient’s disease status.

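### Protocol 4.1 ends disease evaluation at any second-line therapy, against the CT schedule elsewhere in the protocol and the SAP rule that some of these patients need later PD or death for an mPFS event

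*Protocol*

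**What the plan says.** **Stopping rules.** Protocol 4.1 lists what ends disease evaluation: documented PD, "receipt of second-line anticancer therapy for HL (including chemotherapy or radiation), death occurs, or the end of study". Neither response status nor the IRF enters into it. Protocol 7.10 has a narrower rule for mPFS visits. They end at PD, at withdrawal of consent, or at "the start of another anticancer therapy for patients not in CR after completion of frontline therapy". It does not say whose assessment of CR applies.

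**Imaging schedule.** Schedule of Events footnote a follows all treated patients for PFS disease status, with radiology to study closure. Footnote j gives fixed CT days up to Day 2031. Protocol 7.10 also requires CT to study closure, and 4.1 itself gives the same endpoint for follow-up CT shortly before its stopping sentence.

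**Endpoint rule.** Under Protocol 8.1.6.1 and SAP 5.8.1.1, new therapy after completion of frontline therapy is an mPFS event only for non-complete responders confirmed per IRF. For patients who start new therapy "without confirmed noncomplete-response, mPFS will be determined by PD or death" (SAP 5.8.1.2). SAP Table 5-2 censors patients with no documented event at the last adequate assessment, and does the same for an "mPFS event after more than one missed visit".

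**Route into the group.** Protocol 6.4 states: "Patients in PR upon completion of frontline chemotherapy with PET-positive disease may receive radiotherapy". The IRF is not named there, and Protocol 7.4.13 does not require investigators to score Deauville. A site can therefore treat a patient as PET-positive whom the IRF does not confirm as non-CR.

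**The concern.** The SAP rule presupposes that patients who start new therapy without IRF-confirmed non-CR are still imaged. The 4.1 sentence removes imaging from exactly those patients. Two sites could both cite the protocol and collect different primary-endpoint data.

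The new therapy is chosen by an investigator who knows the arm, and it is likely to be given to patients thought to be at higher risk. If such patients drop out of evaluation at that moment, the censoring may be related to prognosis and may be unequal between arms. An IRF-assessed progression that was never imaged cannot be dated after database lock.

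**Working it through.** **1. The plan's own figure.** Protocol 8.1.1: "A total of 260 mPFS events will provide 90% power to detect a hazard ratio of 0.67 at a 1-sided significance level of 0.025". Schoenfeld's formula with 1:1 allocation:

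- Events = 4(1.9600 + 1.2816)² / (ln 0.67)² = 42.03 / 0.1604 = 262.1, rounded up to 263. With HR = ln 0.81 / ln 0.73 = 0.6696, the result is 262.
- Power at 260 events = Φ(√260/2 × 0.4005 − 1.960) = Φ(1.269) = 0.898.

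The figure reproduces and does not depend on the point at issue.

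**2. The rules side by side, for a patient who starts new HL therapy after frontline therapy.**

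| Place | IRF-confirmed non-CR | Not IRF-confirmed non-CR |
|---|---|---|
| Protocol 8.1.6.1, SAP 5.8.1 | mPFS event | no event until PD or death |
| Protocol 4.1 stopping sentence | evaluation ends | evaluation ends |
| Protocol 7.10, mPFS visits | end | end if 'not in CR' means per site; continue if it means per IRF |
| Footnotes a and j, 7.10 CT sentence | CT continues | CT continues |

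In the first column stopping does no harm to mPFS, because the event has occurred. In the second column the protocol gives opposite instructions, and only continued CT fits the SAP.

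**3. One patient followed through.** Take a patient in PR and PET-positive at the site after six cycles, irradiated, with non-CR not confirmed by the IRF. Footnote j puts the first follow-up scans at Days 302, 393, 484 and 575.

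- If the site follows the footnotes and the 7.10 CT sentence, scans continue and later PD is captured. Nothing is lost.
- If the site follows 4.1, the scans at Days 302 and 393 are not done. PD goes unimaged, and Table 5-2 censors the patient at the last adequate assessment, here the end-of-frontline scan. A death after about Day 393 comes after two skipped scans. If those count as missed visits, the death is censored too. If survival or disease-status contacts count as visits, it is an event. The SAP does not say which.

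**4. Size, on stated assumptions.** The documents give neither the share of patients in this group nor their later event rate. I assume a loss of 0% to 10% of mPFS events.

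*Equal loss, analysis at a fixed time.* 260 − 13 (5%) = 247 events gives power 0.882; 260 − 26 (10%) = 234 gives 0.865. If the analysis waits for 260 events, as planned, nominal power stays at 0.898.

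*Timing.* Inputs from Protocol 8.1.1 are "a 2-year mPFS of 81% for patients in the A+AVD treatment group versus 73% for patients in the ABVD treatment group", and "assuming 36 months of accrual, a 5% annual dropout rate, and 24 months of mPFS follow-up after last patient in", with 620 patients per arm. Expected events at month 60 are 620 times the average, over follow-up u uniform on 24 to 60 months, of ∫₀ᵘ h(t) exp(−H(t)) exp(−gt) dt, summed over arms. H(t) is the cumulative hazard, h = −ln(2-year mPFS)/24 up to month 24 and f·h afterwards, and g = −ln(0.95)/12. The plan states only that the event rate falls after 2 years, so f is assumed.

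- f = 0 (complete plateau): 112.1 + 159.5 = 271.6. A 5% loss leaves 258.0, just under 260.
- f = 0.5: 346.6 in total. A 10% loss leaves 311.9, well above 260.

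*Unequal loss, crude approximation.* Apparent HR ≈ 0.67 × (1 − loss in A+AVD) / (1 − loss in ABVD).

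| Loss | Apparent HR | Power |
|---|---|---|
| 5% in ABVD only | 0.705 | 0.79 |
| 10% in ABVD only | 0.744 | 0.64 |
| 5% in A+AVD only | 0.636 | 0.95 |
| 10% in A+AVD only | 0.603 | 0.98 |

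The last two rows are not a gain; they are an exaggerated effect. The approximation ignores the time at risk that is lost along with the events, so it illustrates direction rather than predicts a value.

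**The case against.** The strongest reply is that the protocol as a whole does schedule the scans. Footnotes a and j, the 7.10 CT sentence and 4.1's own imaging schedule all run to study closure, and the stopping sentence sits in an overview section. This stands in part. A reader might infer from 4.1 alone that these patients' events are certain to be lost; the documents do not support that. They support an inconsistency whose effect depends on which text a site follows.

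Second, 'patients not in CR' in 7.10 may be shorthand for the IRF-based component of mPFS, since the Protocol Summary and 4.1 use similar short wording for it. On that reading 7.10 agrees with the SAP. This is plausible, and on either reading patients in CR who start new therapy stay on mPFS follow-up. What remains is that 7.10 should say so.

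Third, deaths are not simply lost. Survival follow-up continues for everyone, and a death counts unless more than one visit was missed. This stands.

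Fourth, SAP Table 5-3 addresses this group directly. One row counts new therapy without confirmed non-CR as progression at the first dose of second-line therapy, another censors it there, and a third restores events after more than one missed visit at their actual date. These rows test sensitivity to the problem and can bring back deaths. They cannot supply PD dates that were never imaged, and they leave the primary analysis as it is.

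**Conclusion.** The 4.1 stopping sentence contradicts the imaging schedule in the same protocol and the SAP's primary-endpoint rule. At sites that follow 4.1, later PD could go unimaged in patients who start new therapy without IRF-confirmed non-CR. Those patients would be censored at the last adequate assessment, and later deaths would be censored too if more than one visit counts as missed. The censoring may be informative and may differ by arm.

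The size cannot be computed from the documents. A reader might be tempted to put a number of lost events on it, but that needs the share of affected patients, their later event rate and the fraction of sites following 4.1, none of which is given. The 5% and 10% losses in the working are assumptions. Because the analysis is event-driven, an equal loss mainly costs time, and threatens the month-60 target only if the plateau after 2 years is close to complete. The more serious risk is bias from unequal loss, which could go in either direction.

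**What to change.** - Reword the 4.1 stopping sentence to agree with footnotes a and j, the 7.10 CT sentence and SAP 5.8.1.2. New therapy should end mPFS disease evaluation only when it is itself an mPFS event, that is, given after completion of frontline therapy to a patient whose non-CR is confirmed per IRF.
- In 7.10, add 'per IRF' to 'not in CR'.
- State that all other patients who start new therapy stay on the CT follow-up already scheduled.
- Leave the existing PD stopping criterion as it is. Requiring IRF-documented PD would keep patients with site-declared PD on scans until the IRF agreed, and this point does not need that.

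The cost is a wording change, and probably a small number of patients who continue CT scans that are already scheduled. One practical matter needs settling: the documents do not describe the IRF end-of-treatment reading being returned to sites. Where a site does not know that non-CR is confirmed per IRF, scheduled CT should simply continue. Once scans continue, whether visits discontinued under 4.1 count as missed in Table 5-2 largely ceases to matter.
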